## PROTOCOL SUMMARY

Title:	A Phase 2 Trial Evaluating the Efficacy of flotetuzumab for Relapsed Acute Myeloid Leukemia (AML) and Myelodysplastic Syndrome (MDS) Following Allogeneic Hematopoietic Cell Transplantation (allo-HCT)
Study Description:	We hypothesize that flotetuzumab for relapsed AML and MDS following allo-HCT will be safe, tolerable and may facilitate preferential immune effector cell retargeting of leukemic cells resulting in improved patient outcomes. Furthermore, administration of a donor lymphocyte infusion (DLI) (if available) in combination with flotetuzumab will be safe, tolerable and may provide additional therapeutic efficacy.
Objectives:	
Primary Objectives:
 
 
• To evaluate the efficacy of flotetuzumab in post-allo-HCT relapsed AML and MDS following Cycle 1 of flotetuzumab (Cycle 1 Day 28 assessment).
 
 
Secondary Objectives:
 
 
• To evaluate the efficacy of flotetuzumab monotherapy in post-allo-HCT relapsed AML and MDS following Cycle 2
 
• To evaluate the safety and tolerability of flotetuzumab +/- DLI in the post-allo-HCT setting.
 

Endpoints:	
Primary Endpoint(s): Efficacy assessed via composite endpoint of CR and CRi (Cycle 1 Day 28 assessment)
 
Secondary Endpoints:
 
 
○ Efficacy assessed at Cycle 2 Day 28 (or at Cycle 1 Day 28 if patient receives only one cycle):             
 
• Composite endpoint of CR and CRi at Cycle 2 Day 28
 
• Overall Response (OR) Rate (defined as PR or greater)
 
• Morphologic leukemia-free state (MLFS) Rate
 
• Partial Response (PR) Rate
 
• Stable Disease (SD) Rate
 
• Progression Free Survival (PFS)
 
• Overall Survival (OS)
 
 
 
○ Safety and Tolerability as assessed by:             
 
• AE Grading per CTCAE v5.0
 
• CRS & Neurotoxicity Grading per ASTCT Consensus Guidelines
 
• Acute GvHD Grading per MAGIC criteria
 
• Chronic GvHD Grading per NIH severity score
 
 
 

Study Population:	The study will enroll adult patients who have been diagnosed with acute myeloid leukemia (AML) or myelodysplastic syndrome (MDS) and have relapsed after allogeneic HCT.
Phase:	Phase 2

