Description of Sites/ Facilities Enrolling:	This is a single institution open label study being conducted at Washington University in St. Louis.
Description of Study Intervention:	Phase 2, single-center, single-arm, open-label trial design evaluating the efficacy of flotetuzumab for the indication of relapsed AML and MDS after allo-HCT
Study Duration:	
 
• Time from study opening to accrual completion – 18 months
 
• Time from accrual completion to primary data analysis – 3 months
 
• Total time from study opening to primary data analysis – 21 months
 
• Time from accrual completion to final data analysis (survival analysis) – 24 months
 
• Total time from study opening to final data analysis – 42 months
 

Participant Duration:	Patients will receive the investigational treatment for the first 28 days of the study (Cycle 1). Based on Day 28 response assessment, patients with CR/CRi will continue investigational treatment for another 28 days (Cycle 2); patients with SD or PR may also continue investigational treatment for another 28 days (Cycle 2) with permission by the investigator. All patients may receive a donor lymphocyte infusion (DLI) concurrent with flotetuzumab in either cycle, at the discretion of the treating physician and investigator; patients with PD at the end of Cycle 1 will come off study. All patients will be followed for 2 years after receiving investigational treatment.

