### **1.3 Overall Study Design and Plan**

This is an open-label, single-arm, single-center Phase 2 study to evaluate for efficacy, safety and tolerability of flotetuzumab administered as a single agent and/or in combination with DLI in patients with relapsed AML post-allo-HCT.

The study is designed to include 2 cycles of treatment. During Cycle 1, patients will be administered flotetuzumab as a continuous IV infusion with a week 1 ramp up to goal/target dose of 500ng/kg/day, which will be continued for the remaining 21 days of a 28-day (4-week) cycle (Cycle 1). Patients found to meet the primary endpoint of complete remission with incomplete hematologic recovery (CRi) or better on their C1D28 response assessment (bone marrow biopsy) will continue on to Cycle 2 of flotetuzumab administered as a continuous IV infusion at a target dose of 500ng/kg/day for an additional 28-day cycle (Cycle 2). Patients found to be deriving clinical benefit as evidenced by stable disease (SD) or a partial remission (PR) on their C1D28 response assessment (bone marrow biopsy) may also continue to Cycle 2 of flotetuzumab at the same dose at the discretion of the treating physician and investigator. Patients may receive a DLI concurrently with flotetuzumab treatment in Cycle 1 and/or Cycle 2 at the discretion of the investigator and treating physician. DLI, if administered, will be given on or after Day 8 of the respective cycle. Of note, if patients are off flotetuzumab for >72 hours between end of C1 and beginning of C2, they will require repeat week 1 ramp up to goal/target dose of 500ng/kg/day. Patients found to have progressive disease (PD) on their C1D28 response assessment (bone marrow biopsy) will proceed off study with SOC. All patients who receive investigational agent will then be followed for treatment response and safety monitoring.

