## 2.0 OBJECTIVES AND ENDPOINTS

Objectives	Endpoints
Primary	
To evaluate the efficacy of flotetuzumab in post-allo-HCT relapsed AML and MDS following Cycle 1 of flotetuzumab (Cycle 1 Day 28 assessment).	Efficacy assessed via composite endpoint of CR and CRi (Cycle 1 Day 28 assessment)
Secondary	

 
• To evaluate the efficacy of flotetuzumab monotherapy in post-allo-HCT relapsed AML and MDS following Cycle 2.
 
• To evaluate the safety and tolerability of flotetuzumab +/- DLI in the post-allo-HCT setting.
 
	
 
• Efficacy assessed at Cycle 2 Day 28 (or at C1 D28 in patients who receive only one cycle):               
 
○ Composite endpoint of CR and CRi at C2 D28
 
○ Overall Response (OR) Rate (defined as PR or greater)
 
○ Morphologic leukemia-free state (MLFS) Rate
 
○ Partial Response (PR) Rate
 
○ Stable Disease (SD) Rate
 
○ Progression Free Survival (PFS)
 
○ Overall Survival (OS)
 
 
 
• Safety and tolerability as assessed by:               
 
○ AE Grading per CTCAE v5.0
 
○ CRS & Neurotoxicity Grading per ASTCT Consensus Guidelines
 
○ Acute GVHD Grading per MAGIC criteria
 
○ Chronic GVHD Grading per NIH severity score
 
 
 

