### 5.5 Definitions of Evaluability

Endpoint	To be evaluable for this endpoint, a patient must...
Efficacy (CR and CRi, C1D28 assessment)	Have completed all Cycle 1 infusions of flotetuzumab (or discontinued treatment due to drug toxicity or disease progression). Patients who are not evaluable for the primary objective will be replaced.
Efficacy (CR and CRi, C2D28 assessment)	Have completed all Cycle 1 and 2 infusions of flotetuzumab (or discontinued treatment due to drug toxicity or disease progression) and undergone C2D28 disease assessment
Efficacy (ORR defined as PR or greater)	Have completed all Cycle 1 infusions of flotetuzumab (or discontinued treatment due to

Efficacy (MLFS rate)	drug toxicity or progression) and undergone C2D28 disease assessment (or C1D28 assessment for patients who only received Cycle 1 treatment).
Efficacy (PR rate)	
Efficacy (SD rate)	
Efficacy (PFS)	
Efficacy (OS)	Have undergone any period of infusion of flotetuzumab
Safety and tolerability (AEs by CTCAE)	
Safety and tolerability (CRS and neurotoxicity by ASTCT)	
Safety and tolerability (acute GVHD by MAGIC criteria)	
Safety and tolerability (chronic GVHD by NIH severity score)	

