## APPENDIX I: Study-Specific DSM Tables

Protocol Objectives and Subject Evaluability	
Objective	# of patients evaluable for this endpoint to date
Primary	
To evaluate the efficacy of flotetuzumab in post-allo-HCT relapsed AML and MDS following Cycle 1 of flotetuzumab (Cycle 1 Day 28 assessment).	
Secondary	
To evaluate the efficacy of flotetuzumab monotherapy in post-allo-HCT relapsed AML and MDS following Cycle 2 (or following Cycle 1 for patients that receive only one cycle).	CR and CRi at C2D28 = ORR = MLFS = PR = SD = PFS = OS =
To evaluate the safety and tolerability of flotetuzumab +/- DLI in the post-allo-HCT setting	AEs = CRS and neurotoxicity = Acute GVHD = Chronic GVHD =

Interim Analysis and Early Stopping Rules
Does the study design include an interim toxicity analysis? No
Does the study design include an interim futility analysis? Yes
If yes, please insert text describing interim futility analysis from the protocol Fifteen patients will be enrolled in the first stage. This cohort will include patients who withdraw from the study for reasons unrelated to drug toxicity. If at least 2 CR/CRi are observed out of the 15 patients, then an additional 10 patients will be enrolled. If 6 or more CR/CRi are observed at the end of study, we would conclude that there is evidence of efficacy to warrant further investigation. There is less than 5% chance to stop the trial at stage 1 if the “true” response is 30% or higher. Conversely, there will be 55% chance to terminate the study early if the true rate is only 10% or less.
If yes, please provide data from the interim futility analysis when completed:
Are there early stopping rules that outline circumstances under which the study must be suspended or closed? Yes
If yes, please insert text describing early stopping rules from the protocol A Bayesian sequential monitoring rule will be implemented for safety. The stopping rule is defined as $\Pr(\theta > \theta_T   \text{data}) > 0.8$ , where $\theta$ denotes the proportion of toxicities (as defined in Section 11.5) and $\theta_T$ denotes the expected serious toxicity rate for study treatments (set as $\theta_T = 20\%$ for non-GVHD toxicity and 25% for GVHD toxicity). Interval analyses will be performed

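### The Section 5.5 evaluability row for CR/CRi at Cycle 2 Day 28 lacks the Cycle 1 Day 28 fallback used elsewhere, so the evaluable (per-protocol) rate drops mainly non-responders and is biased upward by an amount the plan does not fix

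*Combined protocol and SAP*

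**What the plan says.** Section 5.5 sets evaluability endpoint by endpoint. For CR/CRi at C2D28 a patient must "Have completed all Cycle 1 and 2 infusions of flotetuzumab (or discontinued treatment due to drug toxicity or disease progression) and undergone C2D28 disease assessment". The rows that follow (ORR, MLFS, PR and SD rates) require only the Cycle 1 infusions and accept a C2D28 assessment, "or C1D28 assessment for patients who only received Cycle 1 treatment".

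The endpoint definitions carry the same fallback. Section 2.0 heads the list containing this endpoint "Efficacy assessed at Cycle 2 Day 28 (or at C1 D28 in patients who receive only one cycle"), and the Protocol Summary has "Efficacy assessed at Cycle 2 Day 28 (or at Cycle 1 Day 28 if patient receives only one cycle"). The Appendix I objective adds "or following Cycle 1 for patients that receive only one cycle".

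Entry to Cycle 2 depends on the C1D28 response. Patients in CR/CRi go on. For the others, "patients with SD or PR may also continue investigational treatment for another 28 days (Cycle 2) with permission by the investigator", and "patients with PD at the end of Cycle 1 will come off study". Section 1.3 agrees: "Patients found to have progressive disease (PD) on their C1D28 response assessment (bone marrow biopsy) will proceed off study with SOC".

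Section 11.7 plans both an intention-to-treat (ITT) analysis, of everyone given at least one dose, and a per-protocol (PP) analysis, of evaluable patients only. Section 11.8 admits to the efficacy analysis anyone who completed at least one cycle, or who withdrew earlier for a reason possibly related to toxicity. It does not ask for a C2D28 assessment.

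**The concern.** Under the Section 5.5 row, a patient who leaves at C1D28 with progression, or with SD or PR and no second cycle, has no C2D28 marrow and is not evaluable. The clause for patients who stopped because of toxicity or progression does not rescue them, because the C2D28 assessment is an additional condition. Patients in CR/CRi at C1D28 proceed to Cycle 2 and mostly stay in. The set is therefore selected on the outcome being measured, and its size also depends on discretionary decisions about patients with SD or PR.

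The resulting rate would stand beside a Cycle 1 rate based on about 25 patients. It could suggest that a second cycle raises CR/CRi when no further patient has responded. Because the documents also contain a different rule for the same endpoint, the denominator could be settled after the results are known.

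**Working it through.** **The plan's own figure.** The documents state no expected C2D28 rate or denominator, so the only figure to reproduce is the design. Inputs: 10% against 30% CR/CRi, alpha 0.05, power 80% (Section 11.3); 15 then 10 patients, continuing if at least 2 of 15 respond (Section 11.4); success at 6 or more at the end of the study (as worded in Appendix I). Exact binomial calculation gives alpha 0.033, power 0.802, and early stopping probabilities of 0.549 at a true 10% and 0.035 at a true 30%. A minimax search returns the same design, with N = 25. The design rests on C1D28 and does not use the row at issue.

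**Effect of the row.** Let N be the patients evaluable for the primary endpoint, k those without a C2D28 assessment, and x the responders. If none of the k is a responder:

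- rate with the fallback = x / N
- rate under the row = x / (N − k)
- overstatement factor = N / (N − k)

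This factor is an upper limit for a given k. If m of the k were responders at C1D28, they leave the numerator too, and (x − m)/(N − k) is smaller than x/(N − k). The bias is upward as long as responders are rarer among those without C2D28 than overall (m/k < x/N). The Cycle 2 entry rule makes that likely.

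**Illustration.** Take N = 25 and x = 7 at C1D28 (28%, near the 30% target), all 7 holding at C2D28 with no new responses. Intervals are exact (Clopper-Pearson) at the 90% level of Section 11.7. The numbers of SD/PR patients continuing are assumptions.

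| SD/PR patients continuing | With C2D28 | Rate | 90% CI | Factor |
|---|---|---|---|---|
| Fallback kept (all 25) | – | 7/25 = 28% | 14–46% | 1.00 |
| 10 | 17 | 7/17 = 41% | 21–64% | 25/17 = 1.47 |
| 9 | 16 | 7/16 = 44% | 23–67% | 25/16 = 1.56 |
| 6 | 13 | 7/13 = 54% | 29–78% | 25/13 = 1.92 |
| 3 | 10 | 7/10 = 70% | 39–91% | 25/10 = 2.50 |

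If one of the 7 responses is lost by C2D28, the rate over all patients falls to 6/25 = 24%, yet with 13 assessed the row gives 6/13 = 46%.

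**Range of the factor.**

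- Nobody lacks C2D28: 1.0.
- Only CR/CRi patients continue, at the 30% design rate: 1/0.30 = 3.3. (With the whole number 7 of 25 it is 25/7 = 3.6.)
- Proxy from Section 1.2.2: 16 of 23 patients in an earlier study, in a different population, showed anti-leukemic activity. If that share entered Cycle 2, the factor is 23/16 = 1.44. Applied to 25 patients, 25 × 16/23 = 17.4, so about 17 continue and the factor is 1.47. Each such patient who is not continued raises it.

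**The case against.** The strongest reply is that Sections 11.7 and 11.8 already protect the result. The ITT analysis includes every dosed patient, Section 11.8 asks for only one completed cycle, and the endpoint headings carry the fallback. On that view the row is a drafting slip that affects only the PP rate. Most of this stands. A reader might infer from the row that patients leaving at C1D28 vanish from every analysis; the documents do not support that. But Section 11.7 does not say whether ITT or PP leads, names no denominator for the C2D28 rate, and does not say how a one-cycle patient is classified. Appendix I also asks for the number evaluable for this endpoint, so the row feeds the report to the monitoring committee.

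Two other stronger readings fail. A reader might take the row to require that both cycles were given. It does not: it admits patients who stopped for toxicity or progression, and the binding condition is the C2D28 assessment. A reader might also put the overstatement at about two-fold. That needs 12 or 13 of 25 patients without C2D28 (25/13 = 1.92, 25/12 = 2.08), and the documents give no such share.

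Section 2.0 is also not perfectly clear. Under its fallback heading, the CR/CRi bullet carries its own C2D28 timepoint, which the other response bullets do not. That supports calling this a contradiction to reconcile rather than a plain departure from an unambiguous definition.

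Finally, the endpoint is secondary and the analysis descriptive. The per-patient table in Appendix I shows cycles completed and both responses, so the committee could see through a spurious gain. That limits the consequence, but it does not govern how the rate is published.

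**Conclusion.** The point holds in limited form. The C2D28 CR/CRi row conflicts with the endpoint headings in Section 2.0 and the Protocol Summary, the Appendix I objective, the neighbouring rows of Section 5.5, and Section 11.8. Applied as written, it yields an evaluable (PP) rate selected on C1D28 response and biased upward by up to N divided by the number with C2D28.

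The size cannot be derived from the documents. It runs from 1.0 to about 3.3, depending on how many patients with SD or PR continue and how many progress. The one available proxy gives about 1.5, on the assumptions that the earlier study's share applies to this population, that every patient with activity enters Cycle 2 and is assessed, and that no responder is lost. The ITT rate, the primary C1D28 endpoint and the Simon design are not affected. Correcting the row is worthwhile but does not bear on the trial's main conclusion.

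**What to change.** 1. In the Section 5.5 row for CR/CRi at C2D28, add the clause the neighbouring rows have, accepting C1D28 for patients who received only Cycle 1. All patients evaluable for the primary endpoint then stay in the denominator, and those without CR/CRi count as non-responders.
2. State that a patient who started Cycle 2 but has no C2D28 assessment counts as a non-responder, so that an earlier response is not carried forward.
3. Name this denominator in Section 11.7, say which of ITT and PP is reported first (ITT is the natural choice), and align the Appendix I evaluable count.
4. If a rate among patients who started Cycle 2 is wanted, show it as a descriptive figure with its denominator beside it.

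The cost is a wording change in Sections 5.5 and 11.7 and Appendix I. It needs no new data or visits. The downside is that the reported secondary rate becomes less favourable.

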## 5.6 Concomitant Therapy and Supportive Care Guidelines

All concomitant medications defined below that are administered during the patient's participation in the study must be recorded in the source document and on the electronic Case Report Form (eCRF).

Concomitant Medications that will be recorded in the eCRF:

- Medications related to the management of IRR, CRS and/or Neurotoxicity administered from admission to the hospital for Cycle 1 of flotetuzumab, during Cycle 1 and Cycle 2, and for the 4 weeks following completion of treatment on protocol will be documented in the eCRF.
- Medications and treatments related to the management of CLS administered from admission to the hospital for cycle 1 of flotetuzumab, during Cycle 1 and Cycle 2, and for the 4 weeks following completion of treatment on protocol will be documented in the eCRF
- Immunosuppressive medications and medications related to management of GVHD from the time of study enrollment through 28 days after the last administration of study drug or End-of-Treatment visit, whichever is later, will be documented in the eCRF.

Patients may not receive the following concurrent therapy:

- Any other therapies for leukemia. Use of hydroxyurea or other cytoreductive agents for the purposes of achieving an initial peripheral blast count  $\leq 20,000/\text{mm}^3$  should have ceased by the time of registration. However, hydroxyurea may be reinstated at the discretion of the Investigator for the prevention or treatment of signs or symptoms of leukostasis during the time of study participation. If this occurs, hydroxyurea and any other leukemia therapies used must be recorded in the eCRF.
- Patients may not get treatment with any other investigational agent within 14 days or 5 half- lives, whichever is longer, prior to study drug administration (Cycle 1 Day 1).
- Patients may not receive other investigational drugs during the period of study participation.
- Because flotetuzumab employs a mechanism of action dependent upon the engagement

of T lymphocytes, the use of corticosteroids other than those employed for premedication should be limited as much as possible. Corticosteroid pretreatment should follow the recommended dose and schedule. Steroids may be employed in the treatment of suspected flotetuzumab-associated immunoinflammatory AEs, GVHD/autoimmune AEs or leukemia-associated AEs in consultation with the PI.

- Ruxolitinib should not be administered in patients on active treatment with flotetuzumab without approval from the PI.
- Use of granulocyte colony stimulating factor or granulocyte-macrophage colony stimulating factor is prohibited during Cycle 1. Following Cycle 1, the use of hematopoietic growth factors is still discouraged. However, granulocyte colony stimulating factor or granulocyte-macrophage colony stimulating factor may be used in accordance with the practice of medicine and institutional guidelines at the investigator's discretion.
- Vaccinations (with the exception of the annual inactivated influenza vaccine) are prohibited while patients are actively receiving study drug (i.e. during Cycle 1 and Cycle 2).

Patients may receive the following concurrent therapy:

- Antiemetics, antidiarrheals, anticholinergics, antispasmodics, antipyretics, antihistamines, analgesics, antibiotics and other antimicrobials, histamine receptor (H2) antagonists or proton pump inhibitors, and any other medication intended to treat symptoms or signs of disease not explicitly prohibited as above are allowed.

## **5.7 Women of Childbearing Potential**

Women of childbearing potential (defined as women with regular menses, women with amenorrhea, women with irregular cycles, women using a contraceptive method that precludes withdrawal bleeding, and women who have had a tubal ligation) are required to have a negative serum or urine pregnancy test within 7 days prior to the first dose of flotetuzumab.

Female and male patients (along with their female partners) are required to use a highly effective form of acceptable contraception, defined as those which result in a low failure rate (i.e., less than 1% per year) such as implants, injectables, combined oral contraceptives, intra-uterine devices (IUDs) or vasectomized partner. Male patients with partners of childbearing potential must be either vasectomized or agree to use a condom in addition to having their partners use another method of contraception resulting in a highly effective method of birth control defined as those which result in a low failure rate (i.e., less than 1% per year) such as implants, injectables, combined oral contraceptives, or IUDs. Patients must agree to use contraception during participation in the study and for 12 weeks following the last dose of flotetuzumab. Patients should also abstain from sperm/egg donation during the course of the study.

If a patient is suspected to be pregnant, flotetuzumab should be immediately discontinued. In addition, a positive urine test must be confirmed by a serum pregnancy test. If it is confirmed that the patient is not pregnant, the patient may resume dosing.

If a female patient or female partner of a male patient becomes pregnant during therapy or within 12 weeks after the last dose of flotetuzumab, the investigator must be notified in order to facilitate outcome follow-up.

